8.2.9 Severity

The Investigator will determine the intensity of each AE using the following terms and definitions:

Mild: An AE that was usually transient required no intervention or special treatment and did not interfere with usual/normal activities.

Moderate: An AE that interfered with usual/normal activities but was ameliorated by therapeutic measures.

Severe: An AE that was intense or debilitating and which interfered with usual/normal activities. Recovery was usually aided by therapeutic measures. Discontinuation of IMP might have been required.

8.3 Reporting of Adverse Events

All AEs that occur between randomization through Day 28 visit will be reported. AEs that start prior to study drug administration will also be captured. Worsening signs and symptoms of the underlying disease will be reported as AEs.

The course of each event should be followed until resolution. All unresolved AEs should be followed-up by the Investigator until the events are resolved, or the AE is stabilized and otherwise explained.

AEs should be recorded according to findings and abnormalities detected by the Investigator. Specific capturing of potential secondary infections will take place. In addition, patients should report AEs voluntarily and in response to general, non-directed questioning. For each AE reported by the patient, or observed by the Investigator, the Investigator should obtain all the information required to complete the AE page of the eCRF, in accordance with the guidelines that accompany it.

Atox Bio or designee assumes responsibility for appropriate reporting of SAEs to the regulatory authorities. Atox Bio or designee will also report to the Investigators all SAEs that are unexpected and associated with the use of the drug.

The Investigator must report these events to the appropriate IRB/IEC in accordance with local regulations.

8.4 Reporting of Serious Adverse Events

All SAEs occurring with any patient participating in this clinical study must be recorded. All SAEs must be reported within 24 hours of becoming aware of the event to the Sponsor or designee, with the exception of SAEs that are specifically attributed to underlying disease (see section 8.5). All SAEs beginning within 28 calendar days after the last exposure to IMP must be recorded.

8.4.1 Initial Report

Once an Investigator becomes aware that a SAE has occurred in a study subject, the Investigator (or designate) must complete the information in the SAE screens of the eCRF WITHIN 24 HOURS. The SAE screens will always be completed as thoroughly as possible with all available details of the event. Even if the Investigator does not have all information regarding a SAE, the SAE screens should still be completed within 24 hours. The report should contain, at a minimum, the following information:

- Subject identifiers (i.e., subject number)
- Suspected medicinal product (or if related to IMP, note "AB103/Placebo")
- Adverse event term (must be listed as serious)
- Contact information for person reporting event

Once additional relevant information is received, the SAE screens in the eCRF should be updated WITHIN 24 HOURS.

The medical monitor is available on a 24-hour basis if clinical personnel wish to discuss any safety related events.

8.4.1.1 Electronic SAE reporting system back-up

If the electronic SAE reporting system does not work, the Investigator (or designate) must complete, then date and sign a SAE Report Form and fax it to Atox Bio at [name] within 24 hours.

This back-up system should only be used if the electronic SAE reporting system is not working and NOT if the system is slow. As soon as the electronic SAE reporting system is working again, the Investigator (or designate) must complete the SAE screens in the eCRF within 24 hours. The final valid information for regulatory reporting will be the information reported through the electronic SAE reporting system.

8.4.2 Follow-up and Final Reports

After the initial AE/SAE report, the Investigator is required to proactively follow each subject and provide further information on the subject's condition to CRO.

All SAEs documented at a previous visit/contact and designated as not recovered/not resolved or recovering/resolving will be reviewed at subsequent visits/contacts until the end of the study.

All AEs documented at a previous visit/contact and designated as not recovered/not resolved or recovering/resolving will be reviewed at subsequent visits/contacts until study end.

Follow-up information to an initial SAE reports should be reported in the SAE screens of the eCRF within 3 business days. At the time of resolution of a SAE, a final report must be provided to the Sponsor by completing the appropriate SAE Report Form.

Any AE, regardless of severity, and whether or not ascribed to the IMP administration, will be recorded as such using medical terminology in the source documentation and on the appropriate eCRF. Whenever possible, diagnoses should be given when signs and symptoms are due to a common etiology (e.g. nausea and vomiting should be reported as "gastroenteritis" if gastreoenteritis is the etiology of both). However, worsening sign(s) and symptom(s) of a diagnosis should be recorded separately. Patients withdrawn from the study due to AEs will be followed by the Investigator until the outcome is determined and, when appropriate, additional written reports and documentation will be provided.

All SAEs that have not resolved by the end of the study, or that have not resolved upon discontinuation of the patient's participation in the study, must be followed-up until either:

- the event resolves
- the event stabilizes
- the event returns to baseline, if a baseline value is available
- the event can be attributed to agents other than the study drug, or
- the event can be attributed to factors unrelated to study conduct
8.5 Disease Related Adverse Events

It is recognized that the patient population with NSTIs who require critical care support will experience a number of common aberrations in laboratory values, signs, and symptoms due to the severity of the underlying disease and the impact of standard therapies. These will not necessarily constitute an AE unless they require significant intervention, lead to discontinuation of blinded study medication, felt to be related to blinded study medication or are considered to be of concern, in the Investigator's clinical judgment. Examples of the type of AEs that may be associated with the initial NSTI event are listed below.

8.5.1 List of Expected Adverse Events

Acute respiratory failure; respiratory distress; acute lung injury; acute respiratory distress syndrome (ARDS); acute renal failure; coagulation dysfunction; decreased platelet count; neutropenia; hypothermia; fever, bacteremia; sepsis, septic shock; hypotension; metabolic acidosis, pleural effusion; abdominal compartment syndrome; repeated surgeries/debridement; amputation.

For purposes of this study, deaths will be captured as clinical outcomes and do not need to be reported as SAEs unless felt related to study drug administration.

8.6 Safety Monitoring

The study medical monitor will assess all SAEs on an ongoing basis. Attention will be given to SAEs assessed as drug-related. The medical monitor may request unblinding of the treatment allocation of a patient for regulatory reporting purposes. The medical monitor will convene the DMC on ad-hoc basis if safety concerns arise from the medical monitor review.

8.7 Independent Data Monitoring Committee (iDMC)

An iDMC will be established to evaluate the safety of the study.

An iDMC review of the safety data is planned after 50, 100 and 200 patients have completed 28 days of the study. Futility analyses will also be performed after 100 patients have completed 28 days. After completion of the study the iDMC will meet again to evaluate the full study safety data and provide their evaluation to the Sponsor.

For each planned iDMC review, all safety data on all patients who received one dose of AB103 will be made available to the iDMC. The data reviewed by the iDMC will be unblinded and presented by group to facilitate recommendations to the Sponsor. Data submitted to iDMC review will be unaudited. A designated unblinded statistician will provide unblinded safety data to the DMC using programs constructed and validated by the blinded Study Statistician and Statistical Programming Team. Further details on data management will be provided in the statistical analysis plan (SAP).

The iDMC may also meet on an ad-hoc basis when immediate safety concerns arise. In case of urgency, the chair of the committee could address any questions or concerns regarding the safety of the patients.

9. STATISTICS

9.1 Synopsis of Key Statistical Approaches

9.1.1 Primary Efficacy Comparison

The primary efficacy comparison involves testing the following superiority hypotheses: Ho: $\pi_{0.50} - \pi_{\text{Placebo}} = 0$ vs Ha: $\pi_{0.50} - \pi_{\text{Placebo}} > 0$; where $\pi_{0.50}$ and π_{Placebo} represent the true probability that a patient achieves specific composite clinical success criteria, NICCE, designed to be sensitive to both local and systemic drug effects. Each probability represents the proportion of subjects on each arm expected to respond according NICCE. Success according to NICCE requires meeting all 5 components of the composite endpoint: (i) Alive until Day 28; (ii) Day 14 debridements ≤ 3 ; (iii) No amputation done after the first debridement; (iv) Day 14 mSOFA score ≤ 1 ; and (v) Reduction of ≥ 3 point in mSOFA between Baseline and Day 14. A two-sided α =0.01 will be used to test superiority of AB103 relative to placebo for the primary endpoint (NICCE). A conditional co-primary end point will be tested for superiority if the primary endpoint is significant at a two-sided α =0.01 significance level in order to account for multiple comparisons. A two-sided α =0.05 will be used to test superiority of AB103 relative to placebo for the co-primary endpoint which is defined as (i) Alive at Day 28; (ii) Day 14 debridements ≤3; and (iii) No amputation done after the first debridement. To be considered a success for the co-primary endpoint, patients must meet all 3 components.

9.1.2 Sample Size Justification

This trial will enroll 290 subjects that will be randomized in a ratio of 1:1 to either AB103 0.50 mg/kg (n=145) or placebo (n=145), each in addition to SoC. Sample size analysis was performed assuming that all patients will be evaluable for the primary endpoint. This assumption is justified since all patients in the Phase 2a trial and in the retrospective study were evaluable for NICCE. The primary efficacy hypothesis will be tested using an unadjusted γ^2 statistic with a 0.01 two-sided significance level. Statistical power was computed for a range of expected treatment group differences supported by the results of preliminary studies. For treatment group differences equal to 0.30, 0.25, and 0.20, statistical power will be equal to 99%, 95.9%, and 80.2%, respectively. These estimates were determined conservatively assuming an average success rate of 0.5. In this way these power estimates are applicable across the range of expected response rates but may be conservative in some cases. The use of NICCE and this range of expected treatment effects is supported by preliminary studies. In the Phase 2a trial, 71.4% (5/7) patients with baseline mSOFA≥3 treated with AB103 0.50 mg/kg achieved NICCE. In contrast, 40% (2/5) placebo patients with baseline mSOFA>3 achieved NICCE, a difference of 0.314. The retrospective study provided further support for the untreated response rate. Among 69 patients with baseline mSOFA≥3, 33.3% (23/69) achieved NICCE, difference of 0.381 relative to Phase 2a treated group. If the observed differences are equal to 0.35, 0.25, and 0.20 (centered about 0.5), then the corresponding 2-sided p-values will be p<0.0001, p<0.0001, and p=0.0007, respectively. The observed difference will need to be larger than about 0.16 (e.g., 0.58 vs 0.42) for p≤0.01. Based on a similar evaluation

of the co-primary endpoint, the study is designed to demonstrate statistical significance at two-sided α =0.05 for co-primary success rates of 0.80 vs 0.60 in the AB103 and placebo groups, respectively. If these are the true success rates, then power will 96.4%. However, if the true rates are 0.78 vs 0.62 (difference = 0.16), then power is 84.8%. The sample size has also been selected to obtain sufficient enrollment on the treatment arm for relevant secondary effectiveness endpoints and for safety endpoints.

9.1.3 Futility Analysis

A futility analysis will be performed based on the results of the first 100 patients (50 per group). The futility decision will be based on the predictive probability of eventual study success, conditioned on the data available at interim analysis. Independent, non-informative prior distributions will be used for each parameter: $\pi_{0.50} \sim \text{Beta}(1,1)$, $\pi_{\text{Placebo}} \sim \text{Beta}(1,1)$. The Bayesian predictive probability of study success (i.e., two-sided $p \leq 0.01$) when the remaining patients are finally observed will be determined. The trial will stop enrollment for futility if the predictive probability of study success is below a lower bound threshold of 10%. The following table summarizes what the observed predictive probabilities will be as a function size of the treatment group differences and assuming an observed control success rate of 0.40. If there are 20 success and 30 failures among placebo controls (40% success rate), then the futility boundary will be crossed if the number of active success is 22 (44%) or less. The futility bound is 'non-binding' in the sense that no effort was made to 'recover' alpha to increase power.

Diff	0.000	0.020	0.040	0.060	0.080	0.100	0.120	0.140	0.160	0.180	0.200	0.220	0.240	0.260	0.280	0.300
PP	0.029	0.050	0.082	0.127	0.187	0.261	0.348	0.444	0.543	0.639	0.728	0.804	0.866	0.913	0.946	0.969

9.1.4 Control Of Blinding And IDMC

This study will remain blinded as to treatment allocation. The actual randomized treatment allocations will be kept by a contracted third-party responsible only for managing the randomization process. A variable indicating the blinded treatment allocations will not be part of the clinical study data to be managed by the data management CRO. Therefore, only blinded study data will be available to the primary study statistician and responsible primary programming staff.

An Independent Data Monitoring Committee (iDMC) will be utilized in this study. A detailed iDMC charter will be provided to clarify all relevant issues relating to the conduct of the futility analysis including specific details regarding the operational procedures with fire-walls to protect against potential operational biases. The charter will provide decision rules, composition of the iDMC members and their conflict of interest statements.

A second, unblinded statistician will work with a iDMC to evaluate the unblinded data necessary to perform the futility analysis and to provide to the iDMC other unblinded data such as unblinded safety comparisons as requested by thei DMC. The primary statistical programmer under the direction of the primary study statistician will develop SAS based programs that processes clinical data provided by the blinded data management CRO to populate planned analysis tables and listings. This programming and other relevant

instructions will be made accessible (one-way direction on information flow) to a second statistician. This second statistician will serve as the unblinded statistician. The unblinded statistician will maintain a secured version of the project analysis system not accessible to the primary study statistician or anyone else. The unblinded statistician will obtain the unblinding codes from directly from the randomization vendor. No one will have access to the project analysis system containing the true randomized treatment codes except for the unblinded statistician. The unblinded statistician will therefore be able to efficiently provide unblinded tables and listings developed by the primary study statistician and team directly to the iDMC. The unblinded study statistician will be capable of providing additional unblinded data upon request. The unblinded statistician will perform the necessary computations involving the Bayesian predictive power to be used in the planned futility assessment at the planned interim analysis based on the results from the first 100 evaluable patients. These computations will be performed in accordance to prescribed plans and results provided to the iDMC for the futility assessment. Relevant details will be provided in a separate SAP and in the separate iDMC charter.

9.2 Summary of Other Elements of Analysis Plan

9.2.1 Randomization

290 patients will be recruited into the study and randomized to either 0.5 mg/kg AB103 or placebo in a 1:1 ratio. Randomization will be within site stratified by the diagnosis of Fournier's Gangrene and magnitude of mSOFA score at screening categorized as 3-4 versus >4. In the retrospective study analysis set with baseline mSOFA \geq 3 (N=69), the median value was 4 and 46.6% had values larger than 4. Four computer generated, blocked randomization lists will be provided for each site corresponding to the cross-tabulation of Fournier's Gangrene and baseline mSOFA category status. Within each block, half of the assignments will be to active drug and half to placebo, in random order. Block sizes will be varied.

The following will be done to insure balance through randomization. Every initial randomization code will end in '-1'. If randomization code is used but the patient does not receive drug due to no confirmatory NSTI diagnosis, then the randomization code is not reused. Instead, the next patient from that center meeting the same strata criteria as the non-dosed patient, will receive the same allocation and the same randomization code except that the code will end in '-2'. In this way, randomization codes are not reassigned which can cause confusion but the same allocation is used preserving balance.

9.2.2 Patient Populations

The following analysis sets are defined:

- Intent-to-Treat (ITT): The ITT analysis set will include all randomized patients.
- As-Treated (AT): The AT analysis set will include all randomized patients who were exposed to study medication (active or placebo). The AT analysis

set will be used in primary safety analyses with patients assigned to actual treatment received.

- Modified Intent-to-Treat (**mITT**): The mITT analysis set will include patients who were exposed to study medication and who had a definitive diagnosis of NSTI based on surgical verification. The mITT analysis set will be used in primary effectiveness analyses with patients assigned to their intended randomized assignment.
- Per Protocol (**PP**): Optionally, a PP analysis set may be used in secondary effectiveness analyses. The PP analysis would include patients in the mITT analysis set assigned according to actual treatment received and excluding patients with either 1) significant violations of inclusion or exclusion criteria with potential to confound estimates of drug effects or 2) post randomization protocol violations with potential to confound estimates of treatment effects. Exclusions from the PP analysis set will be determined based on blinded clinical data. The PP analysis may be further restricted to include patients that survive at 3 least days when evaluation critical care variables.

9.2.3 Preliminary And Descriptive Analyses

Before proceeding with between-group comparisons of primary and secondary clinical endpoints, data quality will be assessed by descriptive summaries and graphical methods (e.g., histograms and scatterplots) in order to examine assumptions such as normality that underlie statistical models. Transformations will be used, if needed, to produce variables that conform to the distributional assumptions underlying the analytic techniques employed. For instance, some variables (e.g., physiologic measurements) may be transformed to log scales⁴⁰ to reduce any marked positive skew. Descriptive analyses will be performed in order to characterize the treatment groups and to confirm that the randomization resulted in no clinically significant group differences at baseline. Although emphasis will be on clinical significance, baseline comparisons will include t-tests or Wilcoxon rank sum tests as appropriate for interval variables and chi-square or Fisher's exact tests as appropriate for nominal variables to aid in the screening for baseline differences. Similarly, changes in clinical endpoints overtime will be summarized within each treatment group using summary statistics including mean and median change scores, standard deviations and ranges. Pearson or Spearman rank correlation coefficients will be used to characterize associations among variables within treatment group. When summarizing across groups, partial correlations may be computed controlling for treatment group. For time to event outcomes (i.e., event-free survival), descriptive analyses will include construction of group specific Kaplan-Meier survival curves⁴¹ as appropriate.

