9.2.7 Analysis Of Other Covariate Effects

Covariates will be assessed for potential confounding (due to lack of perfect randomization balance) or effect modification (subgroup efficacy heterogeneity) using multiple logistic regression. Covariates will include but are not limited to age, race, sex, site, and clinical severity scores at baseline. Other baseline variables in which randomization failed to

produce balance between groups will be examined in supporting analyses. This will be done through stratified analyses and multiple logistic regression. Covariate effects on estimates and interactions will be assessed to see if there is evidence of efficacy heterogeneity. Results from all subgroups analyses will be considered hypothesis-generating.

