4.1.2 Blinded Independently Adjudicated AKI Endpoints and Analyses

Reference creatinine values, maximal AKI stage, and AKD stage at Day 14 will be determined by a blinded independent adjudication committee as described in the Clinical Study Protocol. AKI Stage assigned through blinded independent adjudication will be for Maximal stage by KDIGO criteria using creatinine and/or urine output over the first 7 days post screening. For these analyses, subjects with a maximal AKI Stage 2 or AKI Stage 3 will be included. Descriptive comparisons will be made between the Screening (pre-dose) AKI stage and Maximal AKI stage and between the Day 14 algorithmically determined endpoints to the Day 14 independently adjudicated endpoint.

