5.1 Baseline Comparisons

Demographic and baseline characteristics will be summarized for each analysis set overall and by treatment group. Categorical variables including race, ethnicity, and gender will be summarized by counts and percentages. Continuous variables will be summarized using mean, median, standard deviation (SD), and minimum and maximum values. Continuous variables evaluated will include age, BMI, height, weight, systolic BP, diastolic BP, MAP, heart rate, and temperature; as well as ANAYA, LRINEC, and APACHE II scores. Presence of baseline sepsis will be summarized according to the numbers and percentages of patients with baseline cardiovascular and respiratory organ failure as reflected in screening component SOFA scores of 3 or 4. In addition presence of any AKI at baseline algorithmically determined, Stage 2/3 AKI at screening, and maximal AKI Stage 2/3 as assigned by the blinded adjudication panel will be summarized.

Analyses will be performed to confirm that the randomization resulted in no clinically significant group differences at baseline. Although emphasis will be on clinical significance, baseline comparisons will include t-tests or Wilcoxon rank-sum tests as appropriate for interval variables and chi-square or Fisher's exact tests as appropriate for nominal variables to aid in the screening for baseline differences. If there are clinically important baseline differences, multiple logistic regression will be used in supporting analyses to assess the impact of the imbalance on significance levels.

5.2 mSOFA

The Sequential Organ Failure Assessment score or SOFA was originally developed to track a patient's status during a stay in an intensive care unit (ICU)⁸,⁹. Each of six organ systems are evaluated (see Appendix 5) with ordinal scores 0 to 4. A total score is the sum of the component scores. For this study, the liver component is excluded and the resulting sum score is referred to in this study as 'mSOFA'.

Several approaches will be taken to summarize changes over time and between treatment groups in the clinical scores as described below.

mSOFA scores will be assessed as 1) observed cases, 2) last observation carried forward (LOCF), 3) using MMRM, and 4) categorized and combined with mortality and local activity as part of the primary composite clinical success endpoint, NICCE.

The following will be defined as OBSERVED mSOFA.

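### SAP 5.1 lists a largely post-dose variable, maximal AKI stage over 7 days, among the baseline characteristics, so a drug effect on the kidney could be shown as an imbalance and adjusted for in a supporting analysis

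*Protocol*

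**What the plan says.** Protocol 9.2.3 plans descriptive analyses "to confirm that the randomization resulted in no clinically significant group differences at baseline". It adds that "baseline comparisons will include t-tests or Wilcoxon rank sum tests as appropriate for interval variables and chi-square or Fisher's exact tests", and these are meant "to aid in the screening for baseline differences". SAP 5.1 repeats this. Neither document gives a significance level or a decision rule for these tests.

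SAP 5.1 then names the variables. The list closes with three AKI items: any AKI at baseline, Stage 2/3 AKI at screening, and "maximal AKI Stage 2/3 as assigned by the blinded adjudication panel will be summarized". SAP 4.1.2 defines the last of these as "Maximal stage by KDIGO criteria using creatinine and/or urine output over the first 7 days post screening". SAP 8.11 places maximal AKI among the efficacy presentations, by treatment group, in Tables 14.2.6.1.3 and 14.2.6.1.4.

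On consequences, SAP 5.1 says: "If there are clinically important baseline differences, multiple logistic regression will be used in supporting analyses". The stated aim is to see how the imbalance affects significance levels. Protocol 9.2.7 and SAP 5.5 likewise send variables found to be unbalanced to supporting analyses. None of these sections restricts the variables to those measured before dosing. Where the documents differ, the SAP prevails (SAP section 1).

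The confirmatory tests of NICCE and CCPE are unadjusted chi-square tests (SAP 2.1.2 and 2.1.3), and study success rests on those two p-values (SAP 2.2).

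**The concern.** A baseline characteristic should be fixed before treatment can act on it. Maximal AKI stage over the first week is not. The plan itself treats AKI incidence as an outcome: it is a secondary objective in Protocol 2.2 and appears among the secondary endpoints in Protocol 9.2.4.

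If AB103 limits AKI after dosing, the arms will differ on this variable because the drug works. Read as a baseline characteristic, that difference looks like an accident of randomisation, and SAP 5.1 then offers a logistic model to correct for it. Creatinine scores the renal component of mSOFA (Protocol Appendix C), and mSOFA supplies two of the five NICCE components (SAP 5.2.2). Adjusting NICCE for maximal AKI would therefore condition on a step between drug and endpoint, and the supporting analysis could seem to weaken a sound primary result.

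A smaller matter is the baseline p-values. Under randomisation they measure chance only, and they do not show whether an imbalance is prognostic.

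**Working it through.** **Plan's own figures.** The documents give no number for the baseline tests, so the check starts with the stated power. With 145 per arm and the pooled variance under the null, power = Φ((d − z·SE0)/SE1). For NICCE at d = 0.20 (0.60 vs 0.40) and two-sided alpha 0.01:

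- SE0 = √(2 × 0.25/145) = 0.0587
- SE1 = √(2 × 0.24/145) = 0.0575
- power = Φ((0.20 − 2.576 × 0.0587)/0.0575) = 80.2%, as stated

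The same formula gives 95.9% at 0.25 and 99.6% at 0.30 (stated 99%). For the co-primary at alpha 0.05 it gives 96.4% and 84.8%, as stated. These all describe unadjusted tests, so nothing below changes them.

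**How much of the AKI window is post-dose.** The dose is due within 6 hours of diagnosis and the decision to operate (Protocol 4.2.2), and screening evaluation starts at that decision (Protocol 4.3.1). If the 7-day window opens there, the pre-dose share is at most 6/168 = 0.036, under 4% of the time. The documents do not say in what share of patients the maximum is already reached before dosing.

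**What adjustment would do (illustration; all rates assumed).** Let m be the maximal Stage 2/3 rate, and let q1 and q0 be NICCE success with and without it. The q values are the same in both arms, so the drug acts wholly through AKI. NICCE rate = m·q1 + (1 − m)·q0. The flag column is the chance of p<0.05 on maximal AKI; the 0.05 level is also assumed.

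| m placebo / AB103 | q1 / q0 | NICCE placebo / AB103 | True difference | Flagged |
|---|---|---|---|---|
| 0.45 / 0.33 | 0.30 / 0.60 | 0.465 / 0.501 | 0.036 | about 55% |
| 0.50 / 0.30 | 0.20 / 0.60 | 0.40 / 0.48 | 0.08 | 94% |
| 0.60 / 0.30 | 0.10 / 0.70 | 0.34 / 0.52 | 0.18 | nearly 100% |

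First row:

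- placebo NICCE = 0.45 × 0.30 + 0.55 × 0.60 = 0.465
- AB103 NICCE = 0.33 × 0.30 + 0.67 × 0.60 = 0.501
- flag = Φ((0.12 − 1.96 × 0.0573)/0.0569) = 0.55

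In every row the difference within AKI strata is zero. Simulated logistic adjustment (1,500 runs, two-sided 0.01, favourable direction) took the rejection rate from about 12% to 0.6% in the second row and from about 72% to 0.4% in the third. Partial mediation would lose less. If the drug does not affect maximal AKI, adjustment hides nothing.

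**Baseline p-values.** SAP 5.1 names 20 variables: 3 categorical demographics, 9 demographic and vital measures, 3 severity scores, 2 organ-failure items and 3 AKI items. Nineteen are pre-dose. At an assumed 0.05 level, 19 × 0.05 = 0.95 false flags are expected. If the tests were independent, the chance of at least one would be 1 − 0.95^19 = 62%. They are not independent: BMI comes from height and weight, MAP from the two pressures, and Stage 2/3 AKI is part of any AKI. The 62% is therefore too high, though the expected count is not affected.

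**The case against.** The sentence that introduces the tests puts them second: "Although emphasis will be on clinical significance, baseline comparisons will include t-tests or Wilcoxon rank sum tests as appropriate for interval variables". The trigger for adjustment in SAP 5.1 is clinical importance, and a p-value is neither required nor sufficient. SAP 5.1 says only that maximal AKI is summarised; no section names it as a covariate. Every covariate named in SAP 5.5 (age, race, sex, site, APACHE II, Anaya, LRINEC) is pre-dose. Where the SAP does adjust for AKI, in the repeated-measures model of SAP 5.8, it uses Stage 2/3 AKI at screening. SAP 4.1.2 itself separates screening stage from maximal stage. The mITT and Per Protocol sets exclude some randomised patients, so looking at balance in those sets has a purpose.

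All of this stands, and it limits the point. A reader might infer that comparability is judged by significance tests, or that a real effect could be adjusted out of the trial's main result. The documents support neither. The tests are a screening aid with no stated threshold, and both confirmatory tests are unadjusted.

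What the objection does not remove is that the variable sits in the wrong list and that the adjustment provision beside it has no pre-dose limit. A real drug effect on AKI could well be judged clinically important. The case for checking balance in the analysis sets is no reason to include a post-dose variable in the check.

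**Conclusion.** The point holds and is minor. SAP 5.1 misplaces an outcome among the baseline characteristics and leaves open a route by which it could enter a supporting model. Only baseline tables and supporting analyses are exposed. The NICCE and CCPE tests, the sample size of 290, alpha and power are unchanged.

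The size of any distortion cannot be taken from the documents. The illustrations rest on assumed AKI and NICCE rates, full mediation through AKI and a 0.05 flag level that the plan does not contain. They run from no loss (no drug effect on maximal AKI) through 3.6 to 18 points hidden in a supporting analysis. The 3.6-point case is only about 0.6 of a standard error (0.036/0.0587), against the roughly 16-point observed difference that the sample-size section says is needed for p≤0.01. The baseline p-values alone are a matter of tidiness.

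**What to change.** - In SAP 5.1, delete maximal AKI Stage 2/3 from the baseline characteristics and report it with the outcomes, in Tables 14.2.6.1.3 and 14.2.6.1.4. The cross-tabulations against screening stage (14.2.6.1.5 and 14.2.6.1.6) can stay.
- State in SAP 5.1 and 5.5 that baseline tables and covariates for adjusting NICCE and CCPE are limited to variables measured before dosing.
- Base the supporting adjusted analyses on the pre-dose covariates SAP 5.5 already names, whether or not they look unbalanced.
- Optionally, drop the baseline p-values in Protocol 9.2.3 and SAP 5.1 and keep the descriptive statistics by arm.

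If the pre-dose limit is worded for the whole SAP, it must be reconciled with SAP 5.8, which calls Day 1 mSOFA a baseline covariate although Protocol 4.3.2 collects it 16–24 hours after dosing. That is a separate question.

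The cost is a few sentences, plus the p-value columns if the optional step is taken. No data collection, sample size or error rate changes. It should be done before unblinding.
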